Appendix 1: Schedule of Activities (cont.)

Table 5: Post-Treatment Phase

| Assessment/Procedure | Study Drug Discontinuation/Early Termination Visit 28 Days after Last Dose of Study Drug | Post-Tx Follow-Up Period | | Survival Follow-Up Period (Q3M) ^b |
|--|---|--------------------------------|--------------------------------|--|
| | | Q1M up to 2 Years ^a | Q6M up to 2 Years ^a | |
| Serum pregnancy test | x | | | |
| Triplicate 12-lead ECG | x | | | |
| Biochemistry | x | x | | |
| Hematology | x | x | | |
| Urinalysis | x | | | |
| HMRA | x | | x | |
| Bone marrow sampling for HMRA ^c | x | | x | |
| Bone marrow sampling (MRD/Flow, EDTA, PAXgene [®]) ^d | x | | x | |
| Whole blood sampling (EDTA, clinical) | x | x | | |
| FACIT-Fatigue, EORTC Item Library, PRO-CTCAE, EORTC QLQ-C30, EQ-5D-5L ^e | x | | | |
| Concomitant medications | x | | | |
| Adverse events | x | x | | |
| New leukemia treatment | | x | | x |
| Survival follow-up | | | | x |

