2. OBJECTIVES AND ENDPOINTS

This study will evaluate the safety, efficacy, and pharmacokinetics of idasanutlin in the following groups:

- Idasanutlin in combination with cytarabine and daunorubicin (7+3 regimen) in induction, idasanutlin in combination with cytarabine in consolidation, and single-agent idasanutlin in maintenance in patients with newly diagnosed, previously untreated AML
- Idasanutlin as a single agent in maintenance for idasanutlin treatment-naïve patients who received induction and chemotherapy consolidation for AML outside the study and had MRD-positive remission after induction

This study is composed of a dose-escalation phase, an expansion phase, and a post-consolidation phase (see [Figure 2](#)).

Specific objectives and corresponding endpoints for the study are outlined below.

In this study, "study treatment" refers to the protocol-mandated treatments under study (i.e., idasanutlin, cytarabine, and daunorubicin).

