Table 1 Treatment during the Dose-Escalation Phase

| Cycles | Drug Regimens |
|---|--|
| Induction Up to 2 cycles ^a | 
 • Cytarabine 200 mg/m² IV on Days 1–7 • Daunorubicin 60 mg/m² IV on Days 1–3 • Idasanutlin TBD QD (starting dose 200 mg) orally on Days 1–5 |
| Chemotherapy consolidation or allo-HSCT (per investigator discretion): | |
| Chemotherapy Up to 4 cycles | 
 • Cytarabine 1.5 g/m² IV on Days 1–5 administered over 3 hours • Idasanutlin TBD ^b QD orally on Days 1–5 |
| Allo-HSCT | 
 • As per local guidelines |
| Maintenance Cycles 1–12 ^c | 
 • Idasanutlin 150 mg QD orally on Days 1–5 ^d |

allo-HSCT = allogenic hematopoietic stem cell transplant; QD=once a day; TBD=to be determined.

^a Cytarabine/daunorubicin doses/regimen can be lowered in the second cycle as per site guidelines.

^b Dose in consolidation will be determined by the Sponsor after determination of all available data. It will not exceed induction dose.

^c On the basis of safety, tolerability, and clinical benefit and after consultation with the Medical Monitor, intra-patient escalation may be allowed to 200 mg.

^d On the basis of safety, tolerability, and clinical benefit and after consultation with the Medical Monitor, patient may be allowed to continue maintenance at the same dose within past the 12 cycles

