Appendix 1: Schedule of Activities (cont.)

Table 1: Induction (cont.)

| Assessment/Procedure | Screening ^a | Induction (28-Day Cycle) up to 2 Cycles | | | | | | | | | | |
|---|------------------------|---|----|----|----|----|----|----|-----|-----|-----|-------------------|
| | Days –14 to –1 | D1 | D2 | D3 | D4 | D5 | D7 | D8 | D15 | D22 | D28 | |
| | | | | | | | | | | | | |
| EORTC QLQ-C30, EQ-5D-5L ^k | | x ^l | | | | | | | | | | |
| HMRA | | | | | | | | | | | | x ^f |
| Bone marrow sampling for HMRA ^m | x | | | | | | | | | | | x ^f |
| Bone marrow sampling ⁿ (MRD/Flow, EDTA, PAXgene [®]) | x | | | | | | | | | | | x ^f |
| Whole blood sampling (flow, EDTA, clinical) | x | x | | | | | | | | | | x ^{f, o} |
| Whole blood sampling PAXgene | | x | | | | | | | | | | |
| RBR sampling/blood serum and plasma (optional) | x | | | | | | | | | | | |
| PK sampling and MIC-1 | | Refer to Appendix 2 | | | | | | | | | | |
| Concomitant medications | x | To be recorded continually; see Section 4.4 | | | | | | | | | | |
| Adverse events | | To be assessed continually; see Section 5.3.1 | | | | | | | | | | |
| Daunorubicin treatment (60 mg/m ² IV) ^p | | x | x | x | | | | | | | | |
| Idasanutlin treatment (PO QD) ^p | | x | x | x | x | x | | | | | | |
| Cytarabine treatment (200 mg/m ² IV) ^p | | x | x | x | x | x | x | | | | | |

AML=acute myeloid leukemia; CT=computed tomography; CTCAE=Common Terminology Criteria for Adverse Events; ECHO=echocardiogram; ECOG=Eastern Cooperative Oncology Group; eCRF=electronic Case Report Form; EDTA=ethylenediaminetetraacetic acid; EOI=end of induction; EORTC=European Organisation for Research and Treatment of Cancer; EORTC QLQ-C30=EORTC Quality-of-Life Questionnaire–Core 30; EQ-5D-5L=EuroQol 5-Dimension, 5-Level; FACIT=Functional Assessment of Chronic Illness Therapy; HMRA=hematologic malignancy response assessment; MRD=minimal residual disease;

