Appendix 1: Schedule of Activities (cont.)

Table 1: Induction (cont.)

MUGA=multiple-gated acquisition (scan); PK=pharmacokinetic; PO=orally; PRO=patient-reported outcome; PRO-CTCAE=Patient-Reported Outcomes Common Terminology Criteria for Adverse Events; QD=once a day; RBR=Research Biosample Repository; TB=tuberculosis.

- ^a The screening period starts with the signing of the Informed Consent Form, including the optional Informed Consent Form if appropriate. Results of standard-of-care tests or examinations performed prior to obtaining informed consent and within the defined window may be used as screening and baseline assessments; such tests do not need to be repeated for screening purposes.
- ^b Informed consent must be documented before any study-specific screening procedure is performed.
- ^c Must be performed within 7 days of the planned D1
- ^d If a chest CT is performed up to 28 days prior to study drug administration, a chest X-ray is not required. Patients with a medical history of fungal and TB infections should have a chest CT performed within 28 days prior to study drug administration.
- ^e Vital signs include body temperature, systolic and diastolic blood pressure, pulse rate and respiratory rate. Body surface area will also be measured at screening.
- ^f Should Day 28 not be the last day of the cycle the following will be assessed every 7 days following D28 until end of cycle: biochemistry, hematology, vital signs, ECOG performance status. Bone marrow, HMRA and whole blood sampling should be repeated on the last day of the cycle with D56 as the limit and if not performed within the previous 2 weeks.
- ^g All ECGs should be performed within 2 hours prior to idasanutlin administration and 6 hours after idasanutlin administration.
- ^h Includes systems of primary relevance (e.g., cardiovascular and respiratory systems), systems associated with symptoms (newly emergent or monitored from baseline), and areas associated with tumor assessment (lymph nodes, liver, spleen, and any other areas identified at baseline). Record new or worsened clinically significant abnormalities on the Adverse Event eCRF.
- ⁱ Includes hepatitis B surface antigen, total hepatitis B core antibody, and hepatitis C virus antibody.
- ^j All hematology and biochemistry assessments may be performed up to 3 days prior to the scheduled timepoint. Results must be reviewed by the investigator (or designee) prior to study drug administration.

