Appendix 1: Schedule of Activities (cont.)

Table 3: Maintenance in the Dose-Escalation Cohort and Expansion

| Assessment/Procedure | Maintenance (28-Day Cycle; ± 2 days) All Cycles | | | | | | |
|--|---|----|----|----|----|----------------|----------------|
| | D1 | D2 | D3 | D4 | D5 | D15 | D28 (Q3M) |
| Vital signs ^a , weight, ECOG performance status | x | | | | | | |
| Single 12-Lead ECG ^b | x | | | | | | |
| Targeted physical examination ^c | x | | | | | | |
| Urinalysis | x | | | | | | |
| FACIT-Fatigue, EORTC Item Library, EQ-5D-5L ^d | x ^e | | | | | | |
| PRO-CTCAE, EORTC QLQ-C30 ^d | x | | | | | | |
| Biochemistry ^f | x | | | | | x ^g | |
| Hematology ^f | x | | | | | x ^g | |
| HMRA | x | | | | | | x |
| Bone marrow sampling for HMRA ^h | x ⁱ | | | | | | x |
| RBR sampling Blood serum, plasma (optional) | x | | | | | | |
| Bone marrow sampling for MRD/Flow, EDTA, PAXgene [®] ^j | x ⁱ | | | | | | x |
| Whole blood sampling for EDTA and clinical | x | | | | | | x ^k |
| PK sampling | Refer to Appendix 2 | | | | | | |
| Concomitant medications | To be recorded continually; see Section 4.4 | | | | | | |
| Adverse events | To be assessed continually; see Section 5.3.1 | | | | | | |
| Idasanutlin (PO QD) ^l | x | x | x | x | x | | |

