Appendix 1: Schedule of Activities (cont.)

Table 5: Post-Treatment Phase (cont.)

CTCAE=Common Terminology Criteria for Adverse Events; eCRF=electronic Case Report Form; EDTA=ethylenediaminetetraacetic acid; EORTC=European Organisation for Research and Treatment of Cancer; EORTC QLQ-C30=EORTC Quality-of-Life Questionnaire–Core 30; EQ-5D-5L=EuroQol 5-Dimension, 5-Level; FACIT=Functional Assessment of Chronic Illness Therapy; HMRA=hematologic malignancy response assessment; MRD=minimal residual disease; PRO=patient-reported outcome; PRO-CTCAE=Patient-Reported Outcomes Common Terminology Criteria for Adverse Events; Q1M=once a month; Q3M=once every 3 months; Q6M=once every 6 months; Tx=treatment.

- ^a Patients who discontinue treatment for any reasons other than morphological relapse (see Section 4.5.6) will undergo assessments during the post-treatment follow-up period, which will continue until morphological relapse (see Section 4.5.6) or 2 years, whichever occurs first. The first post-treatment follow-up visit is 1 month after the end of drug discontinuation visit.
- ^b Patients who experience morphological relapse (see Section 4.5.6) or ended their 2 years post-treatment follow-up will be evaluated for survival status and new anti-leukemia treatment every 3 months during the survival follow-up period, which will continue until the end of the study.
- ^c For HMRAs during the study, bone marrow aspirates are required, but bone marrow biopsies may be performed at the discretion of the investigator.
- ^d Bone marrow MRD/Flow, EDTA, and PAXgene to be collected at same time as bone marrow for response assessment. If unscheduled bone marrow aspirate is being collected for hematologic response assessment, then bone marrow MRD/Flow, EDTA, and PAXgene samples should also be collected. If any MRD assessments are done locally, please record this information in the eCRF. The priorities are MRD/FLOW > EDTA > PAXgene.
- ^e PRO questionnaires need to be self-administered before the patient receives any information on disease status. Completion of PROs should occur prior to the performance of non-PRO assessments whenever possible. PRO assessments include the FACIT-Fatigue, EORTC QLQ-C30, EORTC Item Library symptoms, PRO-CTCAE, and EQ-5D-5L.

Appendix 2

Schedule of Pharmacokinetic and PD Biomarker Samples

Table 1 All Cohorts

| Study Visit | | Plasma Idasanutlin PK Sample | Serum MIC-1 Sample | Plasma Cytarabine PK Sample | Plasma Daunorubicin PK Sample |

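### Table 5 of the activity schedule requires a marrow at the discontinuation visit with no exemption for a recent sample, so a patient stopping after a standard induction cycle is scheduled for two aspirates 5 to 7 days apart

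*Combined protocol and SAP*

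**What the plan says.** Appendix 1, Table 5 has one end-of-treatment column, the "Study Drug Discontinuation/Early Termination Visit 28 Days after Last Dose of Study Drug". It marks the hematologic response assessment (HMRA), marrow for that assessment, and marrow for MRD/Flow, EDTA and PAXgene. Footnote c says: "For HMRAs during the study, bone marrow aspirates are required, but bone marrow biopsies may be performed at the discretion of the investigator". Footnote d attaches the biomarker samples to each response marrow. Neither footnote deals with a marrow taken shortly before, and the visit has no stated window.

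The treatment tables also schedule marrow at the end of a cycle:

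- **Table 1**, "Induction (28-Day Cycle) up to 2 Cycles": marrow on Day 28. If the cycle runs longer, footnote f repeats the marrow on the last day, with Day 56 as the limit, only "if not performed within the previous 2 weeks".
- **Table 2**, consolidation: marrow on Day 28. Footnote b rules out a repeat marrow if one was done in the preceding 56 days.
- **Tables 3 and 4**, "Maintenance (28-Day Cycle; ± 2 days) All Cycles" in Table 3: marrow on Day 28 every 3 months, with no cycle numbers given.

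Section 4.5.6 has no general exemption for a recent marrow. It does call for an equivocal marrow to be repeated more than 7 days later.

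**The concern.** A patient whose Day 28 marrow shows treatment failure comes off study drug (Sections 4.5.6 and 4.6.1) and moves to Table 5. Read literally, Table 5 asks for another aspirate about a week after the one that settled the matter. Tables 1 and 2 show that the sponsor meant to avoid closely spaced repeats. That intention is not carried into Table 5.

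Two things are at stake. The first is an avoidable invasive procedure in a population where cytopenia is expected: Table 7 of the protocol cites Grade 3 or higher thrombocytopenia in 98% with 7+3 and 24.5% with idasanutlin. The second is uneven handling across sites. Some will repeat the marrow and some will reuse the Day 28 result, leaving end-of-treatment response and MRD fields filled in different ways or blank. Section 9.2 does not allow a site to ask in advance to depart from the protocol, so the text itself has to settle the question.

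The primary endpoint, CR at the end of induction, is not affected.

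**Working it through.** The documents state no interval between the two marrows, so there is no figure to reproduce. The check is day arithmetic.

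**Inputs**

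- Discontinuation visit: 28 days after the last dose (Appendix 1, Table 5).
- End-of-cycle marrow: Day 28 (Appendix 1, Tables 1 to 4).
- Last dose in induction: "Cytarabine 200 mg/m² IV on Days 1–7" gives Day 7, and idasanutlin ends on Day 5 (Table 1 in Section 3.1.2.2). Section 2 counts all three drugs as study treatment, which favors Day 7; Day 5 applies if the visit is timed from idasanutlin.
- Last dose in consolidation and maintenance: Day 5 (same table, and Tables 4 and 5 in Section 3.1.3).

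**Formula.** With last dose on day d, visit day = d + 28. Gap from the Day 28 marrow = (d + 28) − 28 = d days.

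| Last cycle | d | Visit day | Gap (days) |
|---|---|---|---|
| Induction, from cytarabine | 7 | 35 | 7 |
| Induction, from idasanutlin | 5 | 33 | 5 |
| Consolidation, if a Day 28 marrow was taken | 5 | 33 | 5 |
| Maintenance, if the cycle carries a marrow | 5 | 33 | 5 (3 to 7 if the ±2-day window applies to the marrow) |

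If dosing stops early, the gap shrinks with d; a last dose on Day 3 gives 3 days. All these gaps are under the 14 days of Table 1 footnote f.

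**Consolidation.** Whether a Day 28 marrow exists depends on how the 56-day rule is read. Suppose it looks back across cycles and consolidation starts the day after induction Day 28 (an assumption). Consolidation Cycle 1 Day 28 is then 28 days after the last marrow. Since 28 is less than 56, no marrow is due in that cycle. If the patient then stops, the Day 33 visit is 28 + 5 = 33 days after the last marrow. A 2-week waiver would not cover that visit (33 > 14), but a 56-day waiver would (33 < 56). If the rule covers only repeats within one prolonged cycle, each Day 28 marrow stands and the 5-day gap applies.

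**Maintenance.** The protocol does not say which cycles carry the three-monthly marrow. There are two plausible readings:

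- Cycles 3, 6, 9 and 12: Cycle 12 has a Day 28 marrow, so every patient who completes 12 cycles and stops there has the overlap.
- Cycles 1, 4, 7 and 10, the pattern implied by the questionnaire footnote (every 3 months from Cycle 1): Cycle 12 has none, so no such completer has it.

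On either reading, 4 of the 12 cycles carry a marrow.

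**Prolonged induction.** The final marrow may be as late as Day 56, so a Day 33 to 35 visit can come before it. The visit still falls 5 to 7 days after the Day 28 marrow.

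**The case against.** The strongest reply is that this is a matter of schedule convenience, that no analysis changes, and that the overlap is narrower than it first appears. Much of that stands. A reader might infer four stronger things that the documents do not support.

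- **That every consolidation stop produces a duplicate.** The 56-day rule may mean that no Day 28 marrow was taken. The discontinuation marrow is then the first in weeks and is not redundant.
- **That all maintenance completers are affected.** This depends on an unstated anchor, and the answer runs from all to none.
- **That any site reusing one sample is in deviation.** Section 4.5.6 accepts up to 4 days between blood and marrow for one assessment. If the maintenance window covers Day 28, a marrow on Day 29 or 30 is 4 or 3 days before Day 33 and could be paired with that visit's blood. This does not reach the induction gap of 5 to 7 days from a Day 28 marrow.
- **That the second marrow tells nothing, or that these patients are generally thrombocytopenic.** Marrow and counts may still be recovering after induction. Patients in CR have platelets of at least 100 × 10⁹/L (Appendix 19), and post-consolidation entry excludes ongoing Grade 2 or higher hematologic events (Section 4.1.2.3).

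One could also argue that sites will read the 56-day rule as covering the discontinuation visit. They may, but the footnote belongs to Table 2 and does not say so.

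**Conclusion.** The point holds as a minor, inexpensive improvement. Table 5 as written schedules a second aspirate 5 to 7 days after the Day 28 marrow for a patient who stops after a standard 28-day induction cycle, and no text exempts it. This assumes that the patient took all doses of the cycle and had the marrow on Day 28.

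After consolidation the 5-day overlap exists only if a Day 28 marrow was taken under the 56-day rule. In maintenance it exists only if the last cycle carried the three-monthly marrow.

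The number of patients affected cannot be derived from the documents. About 80 is the planned enrollment and so only a ceiling: it includes patients who die, withdraw, stop before Day 28, or stop in a cycle without a marrow. It also includes the 30 post-consolidation patients, who receive no induction on study, so the clear induction case can arise only among the 9–15 + 40 = 49 to 55 others on the planned numbers in Section 3.1.1. Sample size, the primary endpoint and its confidence interval are unaffected.

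**What to change.** Add a footnote to the two marrow rows of Table 5 for the discontinuation visit, along these lines: *Marrow sampling need not be repeated if an evaluable, non-equivocal marrow was obtained within the no-repeat window; the earlier marrow result is then used for this visit. Blood counts and the blood-based HMRA are still performed. An equivocal marrow is repeated under Section 4.5.6.*

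The window should come from the protocol's own rules. The 2 weeks of Table 1 would cover the standard gaps of 5 and 7 days, but it must be reconciled with the 56 days of Table 2, because the two give opposite answers for a marrow 33 days old. Naming the maintenance cycles that carry the three-monthly marrow would also settle whether completers are affected.

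The cost is one footnote. Patients without a recent marrow are still sampled. The downside is that an occasional late marrow change during count recovery would not be captured at that visit.

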Appendix 1: Schedule of Activities (cont.)

Table 5: Post-Treatment Phase (cont.)

CTCAE=Common Terminology Criteria for Adverse Events; eCRF=electronic Case Report Form; EDTA=ethylenediaminetetraacetic acid; EORTC=European Organisation for Research and Treatment of Cancer; EORTC QLQ-C30=EORTC Quality-of-Life Questionnaire–Core 30; EQ-5D-5L=EuroQol 5-Dimension, 5-Level; FACIT=Functional Assessment of Chronic Illness Therapy; HMRA=hematologic malignancy response assessment; MRD=minimal residual disease; PRO=patient-reported outcome; PRO-CTCAE=Patient-Reported Outcomes Common Terminology Criteria for Adverse Events; Q1M=once a month; Q3M=once every 3 months; Q6M=once every 6 months; Tx=treatment.

- ^a Patients who discontinue treatment for any reasons other than morphological relapse (see Section 4.5.6) will undergo assessments during the post-treatment follow-up period, which will continue until morphological relapse (see Section 4.5.6) or 2 years, whichever occurs first. The first post-treatment follow-up visit is 1 month after the end of drug discontinuation visit.
- ^b Patients who experience morphological relapse (see Section 4.5.6) or ended their 2 years post-treatment follow-up will be evaluated for survival status and new anti-leukemia treatment every 3 months during the survival follow-up period, which will continue until the end of the study.
- ^c For HMRAs during the study, bone marrow aspirates are required, but bone marrow biopsies may be performed at the discretion of the investigator.
- ^d Bone marrow MRD/Flow, EDTA, and PAXgene to be collected at same time as bone marrow for response assessment. If unscheduled bone marrow aspirate is being collected for hematologic response assessment, then bone marrow MRD/Flow, EDTA, and PAXgene samples should also be collected. If any MRD assessments are done locally, please record this information in the eCRF. The priorities are MRD/FLOW > EDTA > PAXgene.
- ^e PRO questionnaires need to be self-administered before the patient receives any information on disease status. Completion of PROs should occur prior to the performance of non-PRO assessments whenever possible. PRO assessments include the FACIT-Fatigue, EORTC QLQ-C30, EORTC Item Library symptoms, PRO-CTCAE, and EQ-5D-5L.

Appendix 2

Schedule of Pharmacokinetic and PD Biomarker Samples

Table 1 All Cohorts

| Study Visit | | Plasma Idasanutlin PK Sample | Serum MIC-1 Sample | Plasma Cytarabine PK Sample | Plasma Daunorubicin PK Sample |
|-------------------|-------|---|---|---|---|
| Induction Cycle 1 | Day 1 | Pre-idasanutlin administration (any time prior to dose on that day) | Pre-idasanutlin administration (any time prior to dose on that day) | Pre-idasanutlin administration (any time prior to dose on that day) | Pre-idasanutlin administration (any time prior to dose on that day) |
| | | 30 (±10) min after end of daunorubicin infusion | 30 (±10) min after end of daunorubicin infusion | 30 (±10) min after end of daunorubicin infusion | 30 (±10) min after end of daunorubicin infusion |
| | | 3 hr (±20 min) post-idasanutlin administration | 3 hr (±20 min) post-idasanutlin administration | 3 hr (±20 min) post-idasanutlin administration | 3 hr (±20 min) post-idasanutlin administration |
| | | 6 hr (±20 min) post-idasanutlin administration | 6 hr (±20 min) post-idasanutlin administration | 6 hr (±20 min) post-idasanutlin administration | 6 hr (±20 min) post-idasanutlin administration |
| | | 9 (±1) hr post-idasanutlin administration | 9 (±1) hr post-idasanutlin administration | 9 (±1) hr post-idasanutlin administration | 9 (±1) hr post-idasanutlin administration |
| | Day 3 | Pre-idasanutlin administration (any time prior to dose on that day) | Pre-idasanutlin administration (any time prior to dose on that day) | Pre-idasanutlin administration (any time prior to dose on that day) | Pre-idasanutlin administration (any time prior to dose on that day) |
| | | | 1.5 hr (±10 min) post-idasanutlin administration | | 1.5 hr (±10 min) post-idasanutlin administration |
| | | | 3 hr (±10 min) post-idasanutlin administration | | 3 hr (±10 min) post-idasanutlin administration |
| | | | 6 hr (±20 min) post-idasanutlin administration | | 6 hr (±20 min) post-idasanutlin administration |
| | | | 9 hr (±1 h) post-idasanutlin administration | | 9 hr (±1 h) post-idasanutlin administration |

PK=pharmacokinetic.

